#### Diagnosis and Main Criteria for Eligibility

#### Inclusion Criteria:

A subject must meet all the following inclusion criteria to be eligible for participation in this study:

- 1. Ambulatory male or female outpatients ≥ 18 years of age who have laboratory-confirmed SARS-CoV-2 infection as determined by qualitative PCR (RT-PCR), or other commercial or public health assay approved by regulatory authorities as a diagnostic test for COVID-19 (inclusive of SARS-CoV-2 antigen testing or other approved rapid testing platforms) in any specimen ≤ 5 days prior to randomized treatment. (Note: ≤ 5 days is the post-sampling timeframe from date specimen obtained to administration of blinded study drug).
  - Note: Every effort should be made to reduce this time interval to the minimum as nearly immediate treatment is key for successful intervention. For instance, if SARS-CoV-2 antigen testing is used for diagnostic purposes the subject may be able to receive the study drug the same day testing is performed.
- 2. Asymptomatic with no constitutional COVID-19 illness (evident symptoms), specifically no fever, cough, shortness of breath, fatigue, anorexia, vomiting/diarrhea, headache that is unrelated to pre-existing medical conditions (eg, migraine), sore throat that is unrelated to other pre-existing medical conditions (eg, allergies, gastroesophageal reflux disease), myalgias, olfactory disorders unrelated with previous medical condition, or evidence of pneumonia at Screening.
- 3. Pulse oximetry SpO2 (oxygen saturation) on room air > 94% (i.e., 95% to 100%) at Screening.
- 4. National Early Warning Score (NEWS)  $\leq$  2 points (Appendix 2) at Screening.
- 5. Subject provides informed consent (informed consent form [ICF]) prior to initiation of any study procedures.

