## 7.2.2 Screening/Baseline and Randomized Treatment (Day 1)

All required screening and baseline (pre-IP Day 1) procedures/assessments will be performed prior to administration of the blinded IP.

Briefly the following will occur: Potential eligible participants will be contacted by the Investigator through their database systems for SARS-CoV2 positive subjects nationwide. Since potential participants (SARS-CoV-2 positive subjects) will be confined, they will be contacted over the phone and asked to participate into the clinical trial by providing the oral consent form. After that, the Investigator will review eligibility criteria and if eligible, the screening visit will continue subject's residence. Once there, the Investigator will obtain the written informed consent, eligibility criteria will be reassessed and if eligible, baseline assessments will be performed, and the subject will be randomized to one of the treatment arms. The IP will be administered by an unblinded study nurse at subject's residence. The subject will receive a pulse oximeter for home use and daily recording of SpO2 in order to monitor for development of hypoxia (SpO2 < 94% on room air). Subject will also be instructed to measure, monitor, and record body temperature daily.

Detailed Assessments include the following:

- Informed consent
- Inclusion/exclusion criteria
- Record demography (age [year of birth], age at screening [years], gender [if female, fertility status], race, and ethnicity), disease characteristics (date of exposure, date of onset in terms of date of first potential contact with virus and date of PCR [RT-PCR], or other commercial or public health assay approved by regulatory authorities as a diagnostic test for COVID-19)
- Ordinal Scale assessment
- NEWS (Appendix 2)
- Vital signs (temperature, systolic and diastolic blood pressure, pulse, respiratory rate)
- Measure Body Weight and Height. Calculate Body Mass Index (BMI)
- Record result of historical SARS-CoV-2 PCR (qualitative RT-PCR) or other commercial
  or public health assay approved by regulatory authorities as a diagnostic test for COVID19 in any specimen ≤ 5days prior to Screening (eligibility criterion)
- Record oxygen saturation
- Medical History
- Record presence or absence of any of the following specific conditions which may increase risk of severe COVID-19 disease: Cancer; Chronic kidney disease; COPD (chronic obstructive pulmonary disease); Heart conditions, such as heart failure, coronary

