# 3. INVESTIGATIONAL PLAN

## 3.1 Study Design

This is a prospective, multi-center, randomized (1:1:1), double-blind study of C19-IG 20% at 1 of 2 dose levels versus Placebo in asymptomatic, ambulatory outpatients aged  $\geq$ 18 years who are SARS-CoV-2 positive. Participants will be stratified by age <65 years vs  $\geq$ 65 years of age. The study will enroll asymptomatic subjects with laboratory-confirmed novel coronavirus (SARS-CoV-2) infection as determined by qualitative PCR (reverse transcriptase [RT]-PCR), or other commercial or public health assay approved by regulatory authorities as a diagnostic for COVID-19 (inclusive of SARS-CoV-2 antigen testing or other approved rapid testing platforms) in any specimen obtained  $\leq$  5 days prior to randomized treatment ( $\leq$  5 days is the post-sampling timeframe from date specimen obtained to administration of blinded study drug). Every effort should be made to reduce this time interval to the minimum as nearly immediate treatment is key for successful intervention.

Approximately 801 subjects (267 per arm) will be randomized (1:1:1). Subjects randomized to C19-IG 20% will receive a blinded subcutaneous (SC) infusion on Day 1 at a dose of either 1 gram or 2 grams, according to the randomized dose assigned. Subjects randomized to Placebo will receive a SC infusion of sterile 0.9% sodium chloride injection, United States Pharmacopeia (0.9% NaCl, USP) or equivalent. Blinded study drug will be prepared and administered by an unblinded study nurse who is entirely independent of the evaluating study team with SC infusions using 2 separate syringes as follows:

- Placebo (*two* syringes each containing 5 mL 0.9% NaCl);
- 1 gram C19-IG 20% (one syringe containing 5 mL C19-IG 20% *Plus* one syringe containing 5 mL 0.9% NaCl)
- 2 grams C19-IG 20% (*two* syringes each containing 5 mL C19-IG 20%).

An independent DSMB will review interim safety data when approximately 399 patients have been randomized and treated with follow-up through Day 29 (approximately 133 patients per randomized group).

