# 3.2 Treatment

### 3.2.1 Randomization Scheme and Treatment Arm Assignment

Eligible subjects will be randomized 1:1:1 to Placebo or to C19-IG 20% via a SC infusion on Day 1 at a dose of either 1 gram or 2 grams, according to the randomized dose assigned. A central randomization stratified by age group (age <65 years versus  $\geq$  65 years) will be used for this study. Randomization will be centralized and will be performed via an Interactive Web Response System after subject inclusion. A randomization list containing the randomization numbers and the corresponding randomized treatment assignments will be generated and stored in a secured area that is only accessible to the randomization team.

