#### 6.1 Primary Efficacy Endpoint and Analysis

The primary efficacy analysis will be carried out on the mITT population. The analysis will be repeated using the ITT and PP population if different from the mITT population,

The primary efficacy variable is the proportion of asymptomatic subjects who remain asymptomatic through Day 14. Subject clinical features/symptoms and radiographical evidence of pneumonia will be recorded in the database; the oxygen saturation by pulse oximetry on room air will be recorded daily through Day 14 by subject at home on the "SpO2 and Temperature Log", as well as on the "Patient's Measured Oxygen Saturation" eCRF at the protocol-specified healthcare provider visits. In the case when multiple SpO2 values are recorded on the same day, the lower value will be used for the analysis.

The null hypothesis is that the proportion of subjects who meet the primary endpoint in a given C19-IG 20% dose group (2 g and 1 g) will be no different than the proportion of subjects in placebo group; H0:  $\pi_t - \pi_c = 0$ . The alternative hypothesis is that the proportion of subjects who meet the primary endpoint at Day 14 in a given C19-IG 20% dose group will be different than the proportion

of subjects in placebo;  $H_1$ :  $\pi_t - \pi_c \neq 0$ .

Separate comparisons will be made for each C19-IG 20% dose group. If the 2 g dose group fails to demonstrate superiority compared to placebo at two-sided significance level of 5%, the test for 1 g dose group compared with placebo will be considered as exploratory rather than as confirmatory.

The proportion of subjects who meet the primary endpoint within each treatment group will be presented along with a two-sided exact (Clopper-Pearson) 95% confidence interval (CI).

The observed difference in the proportion of subjects who meet the primary endpoint between each C19-IG 20% dose group and placebo along with the exact unconditional 95% CI for risk difference will be calculated. The null hypothesis will be tested using Chi-square statistic and the p-value will be reported.

Sensitivity analysis on primary endpoint will be performed using the Cochran-Mantel-Haenszel (CMH) test, stratified by randomization strata (age <65 years versus  $\geq$  65 years). The common risk difference in the proportion of subjects meeting the primary endpoint between each C19-IG 20% dose group and placebo, together with the associated 95% CIs and p-value will be presented.

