Subgroup analyses based on the presence of comorbidities associated with increased risk of serious COVID-19 will be performed on the primary endpoint using the method described above with Chi-square test, if appropriate. If data permit, a subgroup analysis based on the number of comorbidities (<2 comorbidities vs. >=2 comorbidities) will also be performed.

Subgroup analyses by perceived comorbidities will include the following conditions: Cancer; Chronic kidney disease; Chronic obstructive pulmonary disease (COPD); Heart conditions, such as heart failure, coronary artery disease, or cardiomyopathies; Immunocompromised state from solid organ transplant; Obesity (BMI of 30 kg/m2) or higher; Diabetes mellitus. The information of subject comorbidity will be recorded on the eCRF.

If for one or more subjects the actual treatment received is different from the randomized treatment and if deemed necessary, sensitivity analysis of the primary efficacy endpoint will be performed by repeating the primary efficacy analysis as described above in this section, but with subjects grouped according to the actual treatment received instead of the randomized treatment.

Data for COVID-19 clinical features/symptoms will be listed and summarized by treatment group at each time point. Radiographic evidence of pneumonia data will be presented in a listing.

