### 6.2 Secondary Efficacy Endpoints and Analyses

### Change in SARS-CoV-2 viral load

Change in SARS-CoV-2 viral load (log10 copies/mL) from Baseline to Day 7 and to Day 14 will be compared between each C19-IG 20% dose group and placebo using the analysis of covariance (ANCOVA) model, including the change from baseline value as a dependent variable; treatment group as a fixed effect; and baseline SARS-CoV-2 viral load value, age and gender as covariates. From this model, the LS means and 95% CIs for each treatment group, the treatment difference in the LS means, the 95% CI for the difference, and the associated p-value will be presented at Day 7 and Day 14.

Subgroup analyses based on the presence of comorbidities associated with increased risk of serious

COVID-19 will be performed on change in SARS-CoV-2 viral load using the method described above with ANCOVA model at Day 7 and Day 14. If data permit, a subgroup analysis based on the number of comorbidities (<2 comorbidities vs. >=2 comorbidities) will also be performed.

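### The planned subgroup analyses repeat the main test within each subgroup and name no treatment-by-subgroup interaction test; age stratum and treatment delay are not examined as effect modifiers

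*SAP*

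**What the plan says.** SAP 6.1 plans subgroups by seven comorbid conditions and, if data permit, by fewer than two versus two or more of them. These analyses "will be performed on the primary endpoint using the method described above with Chi-square test, if appropriate". The method referred to gives, for each dose against placebo, the risk difference with an exact unconditional 95% CI and a chi-square p-value. SAP 6.2 repeats the comorbidity subgroups for change in viral load, "using the method described above with ANCOVA model at Day 7 and Day 14". Protocol 9.1 lists the same seven conditions and describes the purpose as exploratory.

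No treatment-by-subgroup interaction or homogeneity test is named in either document. The only interaction term in the SAP is treatment-by-visit, in the repeated-measures models for the ordinal scale and NEWS.

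Age is the sole stratification factor (SAP 3.2.1: "A central randomization stratified by age group"). For the primary endpoint it enters once: "Sensitivity analysis on primary endpoint will be performed using the Cochran-Mantel-Haenszel (CMH) test", which yields one common risk difference. Age is also a covariate in several secondary models. No subgroup by age is planned.

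On timing, SAP 3.1 says "Every effort should be made to reduce this time interval to the minimum as nearly immediate treatment is key for successful intervention", and the protocol says the same. Up to 5 days are allowed; the protocol's inclusion criteria explain that this "is the post-sampling timeframe from date specimen obtained to administration of blinded study drug". Protocol 7.2.2 has sites record "date of onset in terms of date of first potential contact with virus and date of PCR" or another approved assay. Delay is not a subgroup, covariate or sensitivity factor in any planned analysis.

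**The concern.** A subgroup analysis is meant to show whether the effect differs between levels of a factor. Separate p-values do not answer that. They depend on how many subjects fall in each level, so a small level will often be non-significant and a large one significant when the effect is identical in both. A reader of such a table could easily conclude that the product works in one group and not in another.

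The choice of factors has a gap as well. The design stratifies on age, but no planned output shows the effect by age. Both documents stress rapid treatment, but no planned output shows the effect by delay. An age or delay analysis added after unblinding would be post hoc and discounted accordingly. What is at stake is the usefulness of the exploratory output, not the primary conclusion.

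**Working it through.** **Inputs.** Control proportion 80%, treated 90%, about 240 evaluable per arm, 10% withdrawal (Protocol 9.2, SAP 10). Two-sided tests at 5% (SAP 4). Seven conditions, a count split and two doses (SAP 6.1). Subgroup shares and comorbidity prevalences are not in the documents; the ranges below are assumptions.

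**The plan's own figures.** With the unpooled formula at two-sided alpha 0.025 and 80% power:

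- 80% vs 90%: n = (2.241 + 0.842)² × (0.8×0.2 + 0.9×0.1) / 0.10² = 9.505 × 25 = 237.6, so 238 per arm.
- 80% vs 85%: 9.505 × 0.2875 / 0.05² = 1093.1, so 1094 per arm.
- Withdrawal: 240 / 0.9 = 267.

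All three match the plan.

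**Power of a within-level chi-square test under a uniform effect.** With n per arm in the level,

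power = Φ[(0.10 − 1.96·√(2×0.85×0.15/n)) / √(0.25/n)].

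For n = 240 this is Φ[(0.10 − 0.0639)/0.0323] = Φ(1.12) = 87%.

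**Chance of discordant p-values.** The two levels contain different subjects. If a and b are their powers, the chance that exactly one is significant is a(1−b) + b(1−a). For a 5% share (12 and 228 per arm): 0.099×0.149 + 0.851×0.901 = 0.78.

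**Power of an interaction test.** A Wald test on the difference between two risk differences has k = |d₁−d₂| / √(v₁+v₂), with v = [0.16 + (0.8+d)(0.2−d)]/n, and power Φ(k−1.96) + Φ(−k−1.96). For a 50% share and +10 versus 0 points: k = 0.10/√(0.25/120 + 0.32/120) = 1.45, so power is 31%.

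| Share of subjects in level | Power in level | Power in the rest | One significant, other not, same true effect | Interaction power, +10 vs 0 points | Interaction power, +15 vs +5 points |
|---|---|---|---|---|---|
| 5% | 10% | 85% | 78% | 10% | 11% |
| 10% | 16% | 83% | 73% | 15% | 17% |
| 20% | 28% | 79% | 63% | 23% | 26% |
| 30% | 39% | 73% | 55% | 28% | 31% |
| 50% | 58% | 58% | 49% | 31% | 34% |

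The discordance column assumes that both levels are tested. The SAP names both levels only for the count split; for the seven conditions it does not say whether subjects without the condition get their own test.

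**Under no effect at all.** Seven conditions × 2 doses = 14 tests among subjects with each condition, or 28 if those without are also tested; the count split adds 2 × 2 = 4, giving 32. If the tests were independent, the chance of at least one p<0.05 would be 1 − 0.95¹⁴ = 51%, 1 − 0.95²⁸ = 76% and 1 − 0.95³² = 81%. They are not independent: the two doses share a placebo arm, and the complement of a rare condition is nearly the whole trial. Simulation with independently assigned comorbidities at assumed prevalences gives about 45% for 14 tests, 52% for 28 and 55–56% for the full set. A false signal in the direction of benefit occurs in only about 25–30% of null trials.

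**The case against.** The plan can be defended on several grounds, and much of the defence stands.

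- The subgroups are labelled exploratory, and confirmatory testing is confined to the two ordered primary hypotheses (SAP 4.5). Type I error for the primary claim is untouched.
- The method carried into the subgroups already includes risk differences with 95% CIs, and nothing in the SAP says that p-values will be compared across levels.
- Age is not ignored: it is the CMH stratifier and a covariate in secondary models.
- An interaction test would have low power.

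Four stronger readings may occur to a reader, and the documents do not support them:

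- *That a spurious claim of benefit is probable.* The independence figures of 51% and 76% count signals in either direction and ignore correlation; the simulated chance of a false benefit is about 25–30%.
- *That early treatment is a question the trial set itself.* No objective or endpoint concerns delay. The remark that "nearly immediate treatment is key for successful intervention" accompanies the enrolment window and asks sites to keep it short.
- *That a null overall result could not be interpreted without a delay analysis.* It would be valid for those enrolled, subjects dosed within 5 days of a positive specimen, and a delay interaction test is unlikely to have the power to settle the matter.
- *That a particular day marks early from late.* Neither document gives a cut-point within the 5 days.

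One practical limit also stands. Protocol 7.2.2 lists the assay date and the historical result but not, in so many words, the specimen date that defines the window.

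What the objection does not remove is that no planned output tests whether the effect differs by any factor, and that neither age nor delay is examined as a modifier at all.

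**Conclusion.** The point holds as a minor improvement to the exploratory analyses. As specified, the subgroup p-values in SAP 6.1 and 6.2 cannot show effect modification. For the primary endpoint, with an identical 10-point effect in everyone, they would disagree between levels in about 49% to 78% of trials for subgroup shares from 50% down to 5%. That rests on 240 evaluable subjects per arm, an 80% control proportion, both levels being tested, and assumed shares. Age stratum and delay are missing from the planned factors although the first is fixed by design and the second can be derived, at least approximately, from recorded dates. The primary test, its error rate and the sample size are not affected.

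**What to change.** Amend the subgroup text in SAP 6.1 and 6.2 before unblinding:

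1. Remove the within-subgroup p-values. Keep, by level and dose, the risk difference (or LS mean difference for viral load) with its 95% CI.
2. Add one treatment-by-subgroup interaction test per factor and dose, on a stated scale and labelled exploratory. For viral load, add the interaction term to the ANCOVA at each visit.
3. Add the randomisation age stratum (<65 versus ≥65 years) as a factor.
4. Add days from specimen collection to dosing as a linear term with its interaction with treatment. If the specimen date is not captured, use the recorded test date and say so. A linear term avoids choosing a cut-point.

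The cost is SAP wording and one model per factor and dose, using data that are already collected or nearly so. There are two downsides. Interaction power is about 10% to 34% in the scenarios shown, so a non-significant result is not evidence of a uniform effect. Interaction p-values also carry multiplicity: eight comorbidity factors plus age and delay, for two doses, make 20 tests on the primary endpoint, and 1 − 0.95²⁰ = 64% is an upper guide to the chance of at least one p<0.05 by chance. The estimates and intervals should therefore lead the report, with the interaction p-values as context.

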### 6.2 Secondary Efficacy Endpoints and Analyses

### Change in SARS-CoV-2 viral load

Change in SARS-CoV-2 viral load (log10 copies/mL) from Baseline to Day 7 and to Day 14 will be compared between each C19-IG 20% dose group and placebo using the analysis of covariance (ANCOVA) model, including the change from baseline value as a dependent variable; treatment group as a fixed effect; and baseline SARS-CoV-2 viral load value, age and gender as covariates. From this model, the LS means and 95% CIs for each treatment group, the treatment difference in the LS means, the 95% CI for the difference, and the associated p-value will be presented at Day 7 and Day 14.

Subgroup analyses based on the presence of comorbidities associated with increased risk of serious

COVID-19 will be performed on change in SARS-CoV-2 viral load using the method described above with ANCOVA model at Day 7 and Day 14. If data permit, a subgroup analysis based on the number of comorbidities (<2 comorbidities vs. >=2 comorbidities) will also be performed.

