Respiratory samples for quantitative measurement of SARS-CoV-2 viral load by NAT or PCR (real-time RT-PCR) (obtained via nasopharyngeal swab) will be obtained for central laboratory analysis on Day 1 prior to blinded IP infusion, and on Day 3, Day 7, Day 14, and Day 29 (± 1 day).

The overall study schema is shown in Figure 4-1.

	Number	ir BIG-CL-PRT-000028	Version 5.0	2.0	Status	Effective	Effective Date 1:	13-Oct-2021	_
_	GC2010 - /	
 
A Multicenter, Randomized, Double-blind, Parallel Group Study to Ev
 
	ble-blind, F	arallel G	sroup Study	r to Evaluate the			_
Q	Safety an	Jp Safety and Efficacy of Anti-COVID-19 Immune Globulin (Human) 20% (C19-IG 20%) versus	une Globul	n (Hum	an) 20% (C	19-IG 20%) versus	Page	51 of 106	

Note: All subjects will receive a pulse oximeter for home use and daily recording of SpO2 in order to monitor for development of hypoxia (SpO2 < 94% on room air). All subjects will also be instructed to measure, monitor, and record body temperature daily. For single dose administrations all doses will be given in 2 syringes to maintain the blind. Note that given the pandemic setting it is likely that Healthcare Provider Visits may consist either of evaluations at the subject's usual residence (home) justified because subject is in confinement or at an alternate site, e.g., Clinic, always under the care and supervision of trained healthcare personnel.

Figure 4-1 Overall Study Schema

CONFIDENTIAL Page 51

	Number	Number BIG-CL-PRT-000028	Version 5.0	Status	Effective	Effective Date	13-Oct-2021
CIVILOLIS	GC2010 - A	Multicenter, Randomized, Double-blind	, Parallel Group Study t	o Evaluate the S	Safety and Efficacy of	~~ ~	901 30 63
Bioscience Industrial Group	Anti-COVID-19	19 Immune Globulin (Human) 20% (C1	9-IG 20%) versus Place	bo in Asympton	natic Ambulatory	Lage	901 10 76

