### 4.4 Handling of Dropouts or Missing Data

Missing data will be treated as missing and no method for imputation is planned for study population or safety analyses except for the partial end dates/times for concomitant medications (Section 5.6) and partial onset dates/times for AEs (Section 7.2.1). When applicable, missing data for binary and selected continuous efficacy endpoints will be imputed using a most conservative/worst case approach, and the related details are described in Section 6.

Missing data on the time to event endpoints will have events coded as right censored per the

following table:

Endpoint	Right Censoring
Time to negative SARS-CoV-2 by PCR	Subjects who did not have negative SARS-CoV-2 by PCR will be right censored as of the date of last non-missing assessment of SARS-CoV-2 by PCR on or prior to Day 29.
Time to Clinical Progression (death, invasive mechanical ventilation, or ICU admission/requiring ICU level of care)	Subjects who did not meet the criteria for clinical progression will be right censored as of the date of last subject contact on or prior to Day 29.
Time to COVID-19 symptoms (fulfillment of the case definition used for the primary efficacy variable through Day 14)	Subjects who did not meet the criteria will be right censored as of the date of last non-missing assessment of clinical features/symptoms on or prior to Day 14.

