#### **Ordinal scales**

a) The absolute value and change from baseline in the Ordinal scale from Day 1 through Day 29 will be summarized by treatment group and visit using descriptive statistics.

Mean change in Ordinal scales through Day 29 will be evaluated by fitting a linear mixedeffects model for repeated measures (MMRM). The model will include change from baseline in Ordinal scale as the repeated dependent variable; treatment (as a class variable), visit (as a class variable), and treatment-by-visit interaction and as fixed effects; baseline Ordinal scale, age and gender as covariates; and measures within subject at each visit as a repeated measure.

An unstructured covariance matrix will be used to model the within-subject error. If the fit of the unstructured covariance structure fails to converge, a compound symmetry covariance structure will be used. Parameters will be estimated using restricted maximum likelihood with the Kenward-Roger method for calculating the denominator degrees of freedom. Data collected at Days 3, 7, 14, and 29 visits will be included in this analysis. Missing data will not be imputed.

From this model, the least-squares (LS) means and 95% CIs for each treatment group, the treatment difference in the LS means, the 95% CI for the difference, and the associated p-value will be reported on Days 3, 7, 14, and 29.

b) The proportion of subjects in each severity category of the 7-point Ordinal scale at Days 1,
 3, 7, 14, and 29 visits will be summarized by treatment group. The difference in severity

category distribution between each C19-IG 20% dose group and placebo at Day 3, Day 7, Day 14, and Day 29 will be examined using proportional-odds cumulative logit model. The cumulative logits model will compare lower ordinal scales to higher ones, or equivalently, less favorable outcomes to more favorable ones. The model may be adjusted for baseline characteristics such as age and gender, if appropriate. The estimated odds ratio and 95% CI will be presented. Graphical illustrations of the fitted model will also be presented for Day 3, Day 7, Day 14, and Day 29.

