### Assessment of clinical severity

The NEWS will be calculated based on 7 clinical parameters and recorded on the eCRF. The absolute value and change from baseline in the total score from Day 1 through Day 29 will be summarized by treatment group and visit using descriptive statistics.

Change in NEWS total score through Day 29 will be evaluated by fitting a linear mixed-effects model for repeated measures (MMRM). The model will include change from baseline in NEWS total score as the repeated dependent variable; treatment (as a class variable), visit (as a class variable), and treatment-by-visit interaction as fixed effects; baseline NEWS total score, age and gender as covariates; and measures within subject at each visit as a repeated measure.

An unstructured covariance matrix will be used to model the within-subject error. If the fit of the unstructured covariance structure fails to converge, a compound symmetry covariance structure will be used. Parameters will be estimated using restricted maximum likelihood with the Kenward-Roger method for calculating the denominator degrees of freedom. Data collected at Days 3, 7, 14, and 29 visits will be included in this analysis. Missing data will not be imputed.

From this model, the least-squares (LS) means and 95% CIs for each treatment group, the treatment difference in the LS means, the 95% CI for the difference, and the associated p-value will be reported for Day 3, Day 7, Day 14, and Day 29.

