#### **Table 2 Sample Size Estimation**

[Sample sizes in table were calculated using https://www.sealedenvelope.com/power/binary-superiority/]

Based on the above extrapolation/estimate, and allowing for a total of 3 arms, randomized 1:1:1 to Placebo and 2 dose levels of C19-IG 20% approximately 801 subjects are allowed to be randomized as part of a humanitarian effort against COVID-19. N=267 subjects per group should allow differentiation in disease evolution for patients randomized to C19-IG 20% versus the control Placebo arm.

Sample size estimation was also calculated with regard to consideration of the viral load first secondary endpoint. A sample size of ~172 patients/arm would theoretically provide the trial with 80% power to detect a difference of 0.5 log10 in the mean reduction of SARS-CoV-2 viral load at a two-sided significance level of  $\alpha = 0.025$ , assuming an expected standard deviation of 1.5 . A 0.5 log10 copies/mL difference in reduction was chosen to represent the minimal threshold for a

biologically relevant change for analyses based on analogy with other viruses. However, it is unknown whether this degree of viral load reduction will be realized as a result of the planned dosages of C19-IG 20% within this clinical setting. The larger sample size per arm provides a greater level of assurance in this regard.

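### Viral load is analysed by separate Day 7 and Day 14 ANCOVAs that ignore earlier post-baseline swabs and give no missing-data rule, although SAP 6.2 specifies an MMRM for NEWS and the ordinal scale

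*SAP*

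**What the plan says.** SAP 6.2 (Change in SARS-CoV-2 viral load) specifies an ANCOVA "including the change from baseline value as a dependent variable; treatment group as a fixed effect", and baseline load, age and gender as covariates. Least-squares means, the treatment difference, its confidence interval and "the associated p-value will be presented at Day 7 and Day 14". The model has no visit term, repeated-measures term or covariance structure. Protocol 9.1 also names ANCOVA for this endpoint, but adjusts for the randomization strata rather than for age and gender.

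Protocol 4.2 schedules quantitative swabs on Day 1 before dosing and on Days 3, 7, 14 and 29.

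Two other endpoints in SAP 6.2 are handled differently. For clinical severity: "Change in NEWS total score through Day 29 will be evaluated by fitting a linear mixed-effects model for repeated measures (MMRM"). For the ordinal scale: "Mean change in Ordinal scales through Day 29 will be evaluated by fitting a linear" mixed model of the same kind. Both use Days 3, 7, 14 and 29, an unstructured covariance and no imputation.

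On missing data, SAP 4.4 says that, when applicable, "missing data for binary and selected continuous efficacy endpoints will be imputed using a most conservative/worst case approach", and refers to Section 6 for details. Section 6.2 gives rules for the oxygen, hospital, ICU and ventilation durations and for mortality. It gives none for viral load.

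Protocol 5.3.4 has withdrawing subjects undergo the Day 14 procedures at an unscheduled visit. The opening of SAP 4 excludes unscheduled visits from the summaries.

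**The concern.** As the text stands, a subject without a Day 14 swab drops out of the Day 14 model, and any Day 3 and Day 7 values that subject supplied are not used. Given the covariates in the model, that analysis is unbiased only if missing the swab is unrelated to the earlier post-baseline load. An MMRM that includes the earlier swabs needs a weaker condition: missingness may depend on any load already observed.

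At stake are the size of the reported Day 14 effect and a little precision on the endpoint that both documents call the first secondary. The SAP gives no reason why this endpoint should have the method that uses less of the data.

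**Working it through.** **Reproducing the plan's figure.** SAP 10 gives about 172 per arm for "80% power to detect a difference of 0.5 log 10 in the mean reduction of SARS-CoV-2 viral load", with SD 1.5 and two-sided alpha 0.025.

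n = 2 × SD² × (z₀.₉₈₇₅ + z₀.₈₀)² / δ² = 2 × 2.25 × (2.241 + 0.842)² / 0.25 = 171.1, which rounds up to 172. The figure reproduces.

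**Inputs from the documents.** Effect 0.50 log10, SD 1.5, 267 per arm, 10% withdrawal (SAP 10); two-sided 5% tests (SAP 4).

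**Assumptions not in the documents.** Correlation of the Day 7 and Day 14 changes 0.3 to 0.7; Day 7 effect −0.50 or −0.25; baseline mean 6 and SD 1.5; 10% to 30% of Day 14 swabs missing; log-odds of missing linear in Day 7 load, slope 1 per log10, with the arm patterns below. The SAP states no expected rate of missed swabs, only the 10% withdrawal.

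**Why bias arises.** Within an arm, the completers' Day 14 mean shifts by the slope of Day 14 on Day 7 load times the difference in mean Day 7 load between completers and all subjects. The bias is the difference of these shifts between arms. If high load is missed under one shared rule and treatment lowers Day 7 load, placebo loses more high-load subjects, its completers look better, and the effect shrinks. If low load is missed, the active arm loses more low-load subjects and the effect again shrinks. With no treatment effect at any visit, a shared rule shifts both arms equally and the bias is nil.

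**Large-sample check** (2,000,000 simulated subjects per setting, two arms, true Day 14 effect −0.50, 10% missing):

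| Missing Day 14 swabs | Day 14 ANCOVA, completers | Shift from −0.50 |
|---|---|---|
| Completely at random | −0.50 | none |
| Same load rule in both arms | −0.47 to −0.49 | 0.01 to 0.03 toward zero |
| High load missed, active arm only | −0.56 to −0.65 | 0.06 to 0.15 away from zero |
| High load missed, placebo arm only | −0.34 to −0.43 | 0.07 to 0.16 toward zero |
| Opposite rules in the two arms | −0.26 to −0.40, or −0.60 to −0.74 | 0.10 to 0.24 either way |

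At 30% missing, the shared rule gives −0.44 to −0.49. The likelihood estimate that also uses Day 7 lies between −0.497 and −0.504 in every setting. For example, with correlation 0.7, Day 7 effect −0.50 and high load missed under one rule, 8.4% of active and 11.5% of placebo swabs are missing; ANCOVA gives −0.468 and the likelihood estimate −0.501.

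**Scale.** With 267 × 0.9 ≈ 240 per arm, SE = 1.5 × √(2/240) = 0.137. A bias of 0.03 is 0.03/0.137 ≈ 0.2 SE. Power at two-sided 5% is Φ(0.50/0.137 − 1.96) = Φ(1.69) ≈ 95.5% without bias, and Φ(0.47/0.137 − 1.96) = Φ(1.47) ≈ 93% at the worst shared-rule value.

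**The case against.** ANCOVA is a standard method and the one that the protocol names. At the documented 10% loss with one shared rule, the bias is about a fifth of a standard error at most and cannot create a false positive when there is no effect at any visit. This stands, and it is why the point is minor.

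The design also works against heavy informative loss. Visits can take place at home, Day 14 assessments are done in hospital for admitted subjects (Protocol 4.2), withdrawing subjects have the Day 14 procedures at withdrawal (Protocol 5.3.4), and viral-load results are withheld from blinded site staff (Protocol 4.3.3). This stands in part: whether the withdrawal swab enters the model is unclear.

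The recovery of −0.50 by the likelihood estimate is by construction, since the data were generated so that missingness depended only on observed Day 7 load. An MMRM does not cure missingness that depends on the unseen Day 14 value, and the check does not cover Day 14 values piling up at the assay floor. Both limits stand.

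A reader might infer that the planned analysis necessarily understates the effect. The documents do not support that: they state no missingness mechanism, and the direction is fixed only if the mechanism is common to the arms. A reader might also infer that the SAP prescribes a complete-case analysis. It never says so. That follows from the silence of 6.2, and 4.4 leaves open whether viral load is among the selected continuous endpoints. Either way the rule has to be written down.

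**Conclusion.** The point holds as a modest improvement. The Day 14 viral-load analysis leaves the Day 3 and Day 7 swabs unused and has no stated missing-data rule, while a better-suited model is specified in the same section. With 10% of Day 14 swabs missing under one load-dependent rule in all arms, the expected bias is about 0.01 to 0.03 log10 toward zero on a 0.50 effect. Rules that differ by arm could move the estimate either way by more, but nothing in the documents indicates such a difference. These sizes rest on the assumed correlations, rates and mechanisms; with swabs missing completely at random there is no bias.

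The endpoint is secondary with no multiplicity adjustment (SAP 4.5), so the confirmatory test of the primary endpoint is untouched.

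**What to change.** In SAP 6.2, make the main viral-load analysis an MMRM on change in log10 load at Days 3, 7 and 14, with:

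- treatment, visit and treatment-by-visit;
- baseline load, age and gender, each crossed with visit (without all these interactions the model does not reproduce the visit-wise ANCOVA when data are complete);
- an unstructured covariance.

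Report the Day 7 and Day 14 contrasts and keep the visit-wise ANCOVA as a sensitivity analysis. State that missing swabs are not imputed in the MMRM. State also whether the swab from the unscheduled withdrawal visit enters the model and, if so, at which visit, so that Protocol 5.3.4 and SAP 4 agree.

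The cost is SAP wording, a little more analysis work and a documented departure from the ANCOVA in Protocol 9.1. The NEWS model is a starting point but not identical: it has no baseline-by-visit term and includes Day 29, and the documents do not say that it has been programmed. Viral load is not among the endpoints listed for the futility analysis in SAP 9, so the interim analysis is not affected.
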